4.4 Sample size calculation

The Simon two-stage design¹⁵ will be used, with a null hypothesis of at most 5% response rate (not warranting further investigation) and an alternative hypothesis of at least 25% response rate (leading to further investigation). The statistical error rates of the design are $\alpha = 0.05$ and $\beta = 0.80$. The first stage consists of 9 patients per cohort ((1) SDC, (2) ACC) evaluable for response. If 0 responses out of the first 9 evaluable patients are observed, the study will be stopped with the conclusion that the drug should not be further investigated. In any other situation, the study will be continued until 17 patients are evaluable for response per cohort. If ≤ 2 responses out of these 17 patients are observed the study will accept the null hypothesis, with the conclusion that the drug should not be investigated further. If > 2 responses out of 17 patients are observed, the null hypothesis will be rejected with the conclusion that the drug should be further investigated. In the third cohort (other SGC) 9 patients will be included to evaluate the efficacy of cabozantinib in other subtypes of c-MET positive SGC. Because different subtypes are included in this cohort, these results are hypothesis forming but will not be used for statistical analysis. Therefore, this study cohort will be closed after the first stage with 9 patients.

Feasibility analysis:

The Radboud university medical center is a tertiary referral center for head and neck cancer and SGC in particular, receiving referrals from all other academic medical centers and the Dutch Cancer Institute in the Netherlands. In 2016 and 2017 approximately 80-90 new locally recurrent or metastatic SGC patients (40% SDC, 40% ACC, 20% other SGC's) visited our outpatient department. Next to this, we closely collaborate with the SGC patient network in the Netherlands. Therefore we believe it is feasible to enroll 17 SDC patients, 17 ACC patients and 9 other SGC patients in two years.

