2. OBJECTIVES

Objectives will be analyzed separately in all 3 cohorts of c-MET positive, advanced SGC: (1) SDC, (2) ACC originated in the salivary glands or other sites of the body, (3) other SGC's

Primary Objective

- Assess the ORR. ORR is defined as the sum of the complete remissions plus partial responses.⁹ The best response will be used in each patient.

Secondary Objectives

- Assess the PFS. PFS will be defined as time from study enrollment until disease progression or death.
- Assess the OS. OS will be defined as time from study enrollment until date of death of any cause.
- Assess the DoR. DoR is defined as time from study enrollment until date of documented tumor progression or death
- Assess the toxicity of cabozantinib. Toxicity will be scored according to NCI CTC common criteria v 4.0.¹⁰
- Assess the QoL of patients treated with cabozantinib using EORTC questionnaires.
- Assess the response rate by using continuous tumor shrinkage end-points, as was advocated by Billingham et al¹¹ and Wason et al.¹²
- ctDNA will be assessed to evaluate whether response and disease progression can be predicted.

More details about the definitions and analysis of primary and secondary outcomes are described in chapter 8.1.

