8.8 Premature termination of the study

The Simon 2-stage design of this study prevents unnecessary exposure of an ineffective treatment. After the first stage (9 patients in each cohort) an interim analysis will be done to see whether continuation of the trial is indicated. See the sample size calculation for more details.

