10.4 Interim analysis

- According to the Simon 2-stage design, interim analysis of treatment efficacy will be done after 9 patients in each cohort. Treatment efficacy will be established by the response rate, in which a treatment response is defined as a complete remission or partial response, based on RECIST version 1.1 criteria. In case of 0 response, this

cohort will be terminated. In case of ≥ 1 response(s), 8 additional patients will be included in stage 2. This interim analysis will be performed by the researcher. The monitor will check the responses, in order to establish whether patients can be included in stage 2.

- For OS, a planned interim analysis will be done after a median follow-up of 3 years. The monitor will analyze interim safety and efficacy data in according to the NFU guideline 'Kwaliteitsborging mensgebonden onderzoek 2.0', for moderate risk studies. Next to this, the monitor will check if the study can proceed to stage 2, based on treatment efficacy in stage 1, as described at the first bullet of this paragraph.

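### Minor: sections 4.4 and 10.4 give the 0-of-9 stop a different scope, 10.4 omits the exemption for the other-SGC cohort, and 4.4 prints the target power as beta

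*Combined protocol and SAP*

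**What the plan says.** **Scope of the stop.** Section 4.4 sets up stage 1 cohort by cohort: "The first stage consists of 9 patients per cohort ((1) SDC, (2) ACC) evaluable for response". Its futility sentence then reads "If 0 responses out of the first 9 evaluable patients are observed, the study will be stopped". Section 10.4, on the same event, says that the "cohort will be terminated. In case of ≥ 1 response(s), 8 additional patients will be included in stage 2". Section 8.8 says that "an interim analysis will be done to see whether continuation of the trial is indicated"; it contains no rule of its own and sends the reader back to 4.4 ("See the sample size calculation for more details").

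**Which cohorts.** Section 10.4 states that "interim analysis of treatment efficacy will be done after 9 patients in each cohort", and its expansion by 8 patients carries no exception. Section 2 counts three cohorts. Section 4.1 lists 9/17 patients for SDC and for ACC but only 9 for other salivary gland cancers (other SGC). Section 4.4 closes that third cohort at 9, treats its results as hypothesis forming, and plans 17 + 17 + 9 patients in its feasibility paragraph.

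**Error rates.** Section 4.4 gives alpha = 0.05 and beta = 0.80 as the design's error rates. Section 10.1 reports a type I error of 0.047 and power of 0.81 at a true response rate of 25%.

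**The concern.** A futility rule should prescribe one action for one result. As written, if SDC had no response in 9 patients and ACC had one or more, 4.4 read literally would end the whole study, while 10.4 would end SDC and take ACC into stage 2. Under 10.4 the researcher performs this look and the monitor checks the responses, and the plan has no DSMB (monitoring paragraph in section 9). The people who apply the rule will therefore know the responses, and its scope should not be left to be settled at that moment.

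The other two items concern the same design statement. Without an exemption in 10.4, one response among the 9 other-SGC patients would literally call for 8 more, in a cohort that 4.4 says is not formally tested. And a type II error rate of 0.80, taken at face value, means power of 0.20, which contradicts 10.1.

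**Working it through.** **Inputs.** From 4.4: null rate 5%, alternative rate 25%, stage 1 with 9 patients, stop at 0 responses, total 17, reject the null with more than 2 responses. From 10.1: type I error 0.047, power 0.81. From 10.4: 8 further patients in stage 2.

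**1. The plan's own figures, one cohort at a time.** With X1 ~ Bin(9, p) and X2 ~ Bin(8, p), the null is rejected when X1 ≥ 1 and X1 + X2 ≥ 3:

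P(reject) = P(X1=1)·P(X2≥2) + P(X1=2)·P(X2≥1) + P(X1≥3)

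- p = 0.05: 0.2985 × 0.0572 + 0.0629 × 0.3366 + 0.0084 = 0.0171 + 0.0212 + 0.0084 = **0.0466**
- p = 0.25: 0.2253 × 0.6329 + 0.3003 × 0.8999 + 0.3993 = 0.1426 + 0.2703 + 0.3993 = **0.8122**

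These match 0.047 and 0.81. The calculation uses nothing from the other cohort, so the match holds whatever the other cohort's response rate. A search over designs with n up to 30 returns 0/9, 2/17 as the Simon optimal design for alpha 0.05 and power 0.80.

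**2. How often the two wordings part.** P(0 of 9) = (1 − p)^9, which is 0.630 at 5% and 0.075 at 25%. For independent cohorts with values za and zb,

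P(exactly one cohort has 0 of 9) = za(1 − zb) + zb(1 − za)

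| True rates (SDC, ACC) | Probability |
|---|---|
| 25%, 25% | 2 × 0.075 × 0.925 = 0.14 |
| 5%, 5% | 2 × 0.630 × 0.370 = 0.47 |
| 5%, 25% (either way round) | 0.630 × 0.925 + 0.075 × 0.370 = 0.61 |

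The expression is linear in za and in zb, so 0.14 and 0.61 are the extremes for rates between 5% and 25%.

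**3. What a literal study-wide stop would do.** Suppose that 0 of 9 in either tested cohort closed both and always voided the other's test. The rejection probability in step 1 is then multiplied by 1 − z of the other cohort. For a cohort with a true rate of 25%:

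- other cohort at 25%: 0.8122 × (1 − 0.075) = **0.75**
- other cohort at 5%: 0.8122 × (1 − 0.630) = **0.30**

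This assumes independent cohorts. The documents do not synchronise accrual; if one cohort had already finished its 17 patients, its loss would be smaller.

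On the other literal reading, the study stops only when both cohorts have 0 of 9. A cohort with 0 of 9 may then go on, and it rejects if it has at least 3 responses in its next 8 patients. This adds P(own 0 of 9) × (1 − z of the other) × P(X2 ≥ 3). With the other cohort at 5% to 25%, power becomes 0.821 to 0.834 and type I error 0.048 to 0.050.

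**4. Enrolment.** Sections 4.1 and 4.4: 17 + 17 + 9 = 43. Section 10.4 applied to all three cohorts: 3 × 17 = 51. The literal trigger, at least one response among the 9 other-SGC patients, has probability 1 − 0.630 = 0.37 at 5% and 1 − 0.075 = 0.925 at 25%.

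**5. Beta.** Attained beta = 1 − 0.812 = 0.19; nominal beta for target power 0.80 is 0.20.

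**The case against.** The best defence is that no careful reader would go wrong. In 4.4 the stop rule stands between two sentences that both speak per cohort, and two tested cohorts have 18 stage 1 patients between them, so a first nine can only belong to one cohort. The same section uses the word study for a single cohort's final test ("If ≤ 2 responses out of these 17 patients are observed the study will accept the null hypothesis"), section 2 says that "Objectives will be analyzed separately in all 3 cohorts of c-MET positive, advanced SGC", and 10.4, the dedicated interim section, states the cohort rule outright. Section 8.8 is general language that already mentions 9 patients in each cohort and does not conflict with 10.4. On other SGC, three statements in 4.1 and 4.4 fix the number at 9. On beta, 10.1 gives the correct power.

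Nearly all of this stands. It settles what was intended and keeps the weight low. It does not remove the mismatch: a decision rule and a stated error rate are wrong as printed, and 8.8 directs the reader to the section with the looser wording.

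A reader might also argue that the per-cohort rule is the only reading that yields both figures in 10.1. The documents do not support that. The hypotheses are at most 5% and at least 25%, so other rates are admissible. With the other cohort at 1%, the both-must-fail reading gives 0.0469 and 0.814; with the other cohort at 50%, the either-closes-both reading gives 0.0465 and 0.811. Both pairs round to 0.047 and 0.81. What can be said is that the per-cohort rule gives the figures without any condition on the other cohort.

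**Conclusion.** The concern holds as a minor inconsistency with clear intent. The same stage 1 result has two printed consequences, and in the case where they differ (exactly one tested cohort with 0 of 9) the probability is 0.14 to 0.61, assuming independent cohorts with true rates between 5% and 25%. The missing exemption in 10.4 and the mislabelled beta are of the same kind.

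Three stronger inferences should not be drawn:

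- *That the trial would run with power of 0.30 to 0.75.* Those values follow only from a study-wide rule that the context does not intend, and only if the stop always voids the other cohort's test.
- *That the trial may enrol 51 patients.* Sections 4.1 and 4.4 set the maximum at 43.
- *That the design has power of 0.20.* Its attained power is 0.81.

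The sample size, the boundaries and the figures in 10.1 are sound.

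**What to change.** - **4.4, stop rule.** Reconcile with 10.4, for example: *If no response is seen in the first 9 evaluable patients of the SDC or ACC cohort, that cohort will be closed; the other cohorts are unaffected and follow their own rules.* The last clause matters: saying merely that the other cohorts continue would literally override another cohort's own 0-of-9 stop.
- **10.4.** Restrict the interim rule and the 8-patient expansion to SDC and ACC, and state that other SGC closes at 9, as in 4.1 and 4.4.
- **4.4, error rates.** Change beta to 0.20 (attained 0.19, power 0.81).
- **8.8 (optional).** Refer to continuation of the cohort concerned and keep the reference to 4.4.

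The cost is a few words in two sections, or three with the optional edit. No design figure has to be recalculated. The change to 4.4 and 10.4 should be in place before stage 1 responses are known.

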5. TREATMENT OF SUBJECTS

5.1 Investigational product/treatment

Patients will use cabozantinib tablets (Cabometyx®) once daily until progressive disease, intolerable toxicity, or investigator and/or patient decision to withdraw for a maximum duration of 2 years.

- Starting dose
 - 60 mg once daily
 - Liver function disorder: 40 mg once daily
 - Renal impairment: Cabozantinib should be used with caution in patients with mild or moderate renal impairment, but no dose reduction is necessary
- Dose reductions
 - Grade 3 or greater toxicities or intolerable grade 2 toxicities: temporary interrupt treatment until side effects recovered to grade 1 toxicity or less. Resume therapy at 40 mg once daily if necessary and at 20 mg once daily at a subsequent episode
 - Dose reductions are recommended for events that, if persistent, could become serious or intolerable.
- Missed dose
 - If there are still 12 hours or more before the next dose is due, then the missed dose should be taken as soon as possible. The next dose should be taken at the normal time.
 - If the next dose is due in less than 12 hours, then the missed dose should not be taken. The next dose should be taken at the normal time.
- Method of administration
 - Cabometyx is for oral use. The tablets should be swallowed whole and not crushed.
 - Patients should be instructed to not eat anything for at least 2 hours before through 1 hour after taking Cabometyx.\

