4.2 Inclusion criteria

In order to be eligible to participate in this study, a patient must meet all of the following criteria:

- Disease specific
 - locally advanced, recurrent, and/or metastatic SGC (excluding sarcomas and mesenchymal tumors)
 - c-MET positive disease (see paragraph 4.1)
 - Measurable disease per RECIST version 1.1
 - Cohort-specific criteria
 - SDC cohort:
 - Direct inclusion (no objective tumor growth prior to inclusion needed)
 - ACC cohort:
 - Inclusion after objective growth in the last three months or complaints due to the disease
 - Other SGC's
 - Inclusion after objective growth in the last three months or complaints due to the disease
- General conditions
 - Age \geq 18 years
 - Eastern Cooperative Oncology Group performance status of 0 or 1.
 - Normal number of neutrophils and thrombocytes
 - Liver function:
 - ALT and AST $<$ 2.5 x upper limit of normal (ULN)
 - Total bilirubin \leq 1.5 x ULN (except for Gilbert's syndrome)
 - Serum albumin \geq 28 g/L
 - Renal function:
 - Creatinine $<$ 1.5 x ULN or calculated creatinine clearance \geq 40 ml/min
 - Urine protein/creatinine ratio \leq 113.1 mg/mmol (\leq 1 mg/mg) or 24-hour urine protein $<$ 1 g
 - Hemoglobin A1c (HbA1c) \leq 8% or a fasting serum glucose \leq 9 mmol/l

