6.6 Dosages, dosage modifications and method of administration

Starting dose of cabometyx is 60 mg once daily (40 mg once daily in case of liver function disorders). Recommended dose modifications are described in paragraph 5.1 of this protocol and table 1 in the Summary of product characteristics (page 4). The trial medication will be stored at the trial pharmacy and can be ordered by filling in an AKF-form. Subsequently, the research nurse of the medical oncology department will hand the medication over to the patient on the outpatient department.

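### Section 5.1 gives one dose-reduction sequence in fixed doses; for patients who start at 40 mg, its first named resumption dose is the dose they were already taking.

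*Combined protocol and SAP*

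**What the plan says.** Section 5.1 lists the starting doses first. The standard is 60 mg once daily, with a separate line reading "Liver function disorder: 40 mg once daily". Section 6.6 says the same: "Starting dose of cabometyx is 60 mg once daily", followed in brackets by "40 mg once daily in case of liver function disorders".

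Under the dose-reduction heading, 5.1 gives the trigger and the first action: "Grade 3 or greater toxicities or intolerable grade 2 toxicities: temporary interrupt treatment until side effects recovered to grade 1 toxicity or less". The resumption rule follows: "Resume therapy at 40 mg once daily if necessary and at 20 mg once daily at a subsequent episode". A second bullet adds: "Dose reductions are recommended for events that, if persistent, could become serious or intolerable". That bullet names no dose level. Nothing under the heading distinguishes patients by starting dose.

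For dose modifications, section 6.6 refers to 5.1 and to table 1 of the SPC. Section 6.5 points to the same two places for dosage. Sections 13.1(d) and 13.1(j) send the management of adverse events to paragraph 6.2 of the Investigator's Brochure. Neither outside document is part of the material reviewed.

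The eligibility criteria in 4.2 allow some abnormality of liver tests: ALT and AST below 2.5 times the upper limit of normal (ULN), and total bilirubin up to 1.5 times ULN, with an exception for Gilbert's syndrome. The protocol gives no threshold or grade for a liver function disorder.

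**The concern.** The sequence of 40 mg and then 20 mg fits a patient who begins at 60 mg. The protocol also provides, twice, for patients who begin at 40 mg, and for them the first named step is the dose on which the toxicity occurred. A reader following 5.1 alone finds no lower dose named for the first episode in this group.

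This deserves attention because the trigger is a toxicity of grade 3 or more, or an intolerable one of grade 2. Section 13.1(j) relies on supportive treatment and dose reductions to manage side effects, and section 9.4 dispenses with a data safety monitoring board. The written rule therefore has to work for every patient the protocol provides for.

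The missing definition adds a second uncertainty. Two investigators could start the same patient at different doses, and the same reduction line would then have a different effect.

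**Working it through.** No sample size, power or error-rate figure bears on this point, and the plan gives no figure of its own to reproduce. The check traces the rule in 5.1 for each starting dose.

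**Inputs**
- Starting doses: 60 mg, or 40 mg with a liver function disorder (5.1 and 6.6).
- Named resumption dose after the first qualifying episode: 40 mg, if necessary (5.1).
- Named resumption dose at a subsequent episode: 20 mg (5.1).

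**Formula**

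Relative reduction = (previous dose − named resumption dose) / previous dose. This takes the named 40 mg step as the one used.

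| Starting dose | First episode | Subsequent episode |
|---|---|---|
| 60 mg | 60 to 40 mg: (60 − 40)/60 = 33% | 40 to 20 mg: (40 − 20)/40 = 50% |
| 40 mg | 40 to 40 mg: (40 − 40)/40 = 0% | 40 to 20 mg: (40 − 20)/40 = 50% |

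The two groups differ in one cell. At the first episode the named step is 20 mg for standard starters and 0 mg for 40 mg starters. At a subsequent episode they are treated alike.

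**Does other protocol text supply a different first step?**
- The words *if necessary* make the 40 mg step conditional, but name no alternative for someone already at 40 mg.
- The second bullet recommends reductions in general and gives no level.
- Section 6.6 repeats the starting doses and otherwise refers elsewhere.

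**Can such patients enter?** The limits in 4.2 admit some raised liver values, so the criteria do not exclude the group outright. Without a definition, the documents do not show how many patients within those limits would start at 40 mg. The only ceiling is total planned enrolment, 17 + 17 + 9 = 43 (section 4.4).

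**The case against.** The strongest reply is that the protocol is not meant to stand alone here. Section 6.6 brings in SPC table 1 beside 5.1, and adverse-event management is delegated to the Investigator's Brochure. Either may cover patients who start at 40 mg, or say what counts as a liver function disorder. This stands as a limit: nothing can be said about those sources. It does not remove the point, because 5.1 states its own explicit sequence, which does not fit one of its own two starting doses.

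A second reply is that the rule is softer than the table suggests. Treatment is interrupted first. The 40 mg step is conditional, and can even be read as letting a standard starter resume at 60 mg, in which case the contrast between 20 mg and 0 mg is not fixed. The general bullet applies to every patient, section 6.1 lists a 20 mg tablet, and nothing forbids going below 40 mg at a first episode. All of this is fair. A reader might infer that the protocol mandates re-challenge at the toxic dose, or denies these patients any reduction; the text supports neither. What remains is that no lower first step is named for them.

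A third reply is that nothing in the analysis depends on this. That is correct. A reader might infer that the gap blurs the reporting of toxicity or of dose reductions. The documents do not support that: toxicity is graded by the NCI criteria (8.2) and summarised descriptively (10.2), and no planned analysis counts dose reductions.

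Finally, the group may be very small, given the liver limits in 4.2 and the albumin requirement of at least 28 g/L. That is also accepted.

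**Conclusion.** The point holds in a narrow form. On the protocol text, the reduction sequence in 5.1 does not work at its first step for patients started at 40 mg: the named change is 0 mg, against 20 mg for standard starters who move to the named step. It is confined to the first qualifying episode and to the resumption dose.

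The conclusion rests on two conditions. The sequence is read as written, in absolute doses for all patients. The SPC table and the Investigator's Brochure are left out of account because they could not be checked; if either settles the matter, the remaining defect is that 5.1 does not agree with it or point to it clearly.

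The number affected cannot be estimated, since the group is undefined. A reader might infer a widespread safety problem from the table above, but the documents give no basis for a large number. The point is worth correcting because it concerns a safety rule and the correction is small. It has no bearing on sample size, the interim look after 9 patients or the final Simon decision.

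**What to change.** Reconcile the starting-dose and dose-reduction passages in 5.1 and 6.6, together with their SPC reference, so that:

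- the sequence is workable for each starting dose the protocol allows;
- it is clear which patients the lower start covers, and how that relates to the liver limits in 4.2;
- it is clear which source governs if 5.1 and the SPC table differ.

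The doses and clinical criteria are for the sponsor to decide; none is proposed here. The cost is a short protocol clarification, with no change to sample size, decision rules or planned analyses.
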